### 1.2.2 Independent Review Facility

MRI scans will be reviewed by a central MRI core laboratory, which will perform the diagnostic reads and assessments of MRI outcome measures. MRI scans should preferably be transferred to the central MRI core laboratory electronically. Data transfer from individual study sites to the central MRI core laboratory may take up to 7-10 days, if not done electronically. Upon receipt of the MRI scans from the study sites, the central MRI core laboratory will provide the diagnostic reads. MRI results must be made available to investigators prior to the dosing visit that the MRI corresponds to (refer to Section 5.1.2 of the study protocol for additional details on MRI safety management).

MRI facility qualification and scan quality control will be performed by the central MRI core laboratory.

In addition to any local reading according to local procedures and requirements, all MRI scans will be reviewed by an expert central reader within approximately 1 week of receipt and a report provided to the site. For the purposes of overall study relevant decisions and recommendations, results from the expert central reader will be used. Any time the central reader identifies a new MRI finding, the study center medical staff and the Sponsor will be rapidly notified (see Section 5.1.2 of the study protocol).

All MRI readings and volume measures will be conducted by the central reader.

### 1.2.3 Data Monitoring

The iDMC will evaluate participant safety on a regular basis. In addition to the data defined in the iDMC Charter (e.g., the incidence and nature of adverse events, serious adverse events, adverse events of special interest, ARIA-E, amyloid-related imaging abnormalities – hemosiderin deposition [ARIA-H], and injection site reactions [ISRs]), the iDMC will review all necessary cumulative data, including efficacy data if necessary, at regular intervals during the study. It is anticipated that these assessments will occur approximately every 3 months or as detailed in the iDMC charter. At the time of each review, the iDMC will make appropriate recommendations (e.g., the study should continue as planned, the safety risk management should be modified, the protocol should otherwise be amended, and enrollment should be held pending further safety evaluations).

Decisions will be made after considering the totality of the available data. Ad-hoc meetings may be called in addition to scheduled meetings, as necessary, to provide recommendations on management of any new safety issues. Specific operational details, such as the committee's composition, frequency and timing of meetings, and members' roles and responsibilities are detailed in the iDMC Charter.

Final decisions will rest with the Sponsor.

In the event the iDMC which reviews safety in both the parent studies (GRADUATE I and GRADUATE II) and POSTGRADUATE is no longer required (for instance after the unblinding of the parent studies) evaluation of participant safety may be taken over by the Sponsor's Internal Monitoring Committee (IMC), with details documented in an IMC Charter.

### 1.2.4 ARIA Management

In POSTGRADUATE, taking into account the evolving experience with managing ARIA findings, including the finding that continued gantenerumab treatment during episodes of asymptomatic mild ARIA-E was not associated with clinically unfavorable outcomes, the Sponsor intends to examine the safety of continuing gantenerumab treatment through mild to moderate asymptomatic ARIA-E findings and to examine the safety of gantenerumab therapy in the presence of an increased number of ARIA-H (microhemorrhages). In the parent studies, treatment was interrupted for participants

with asymptomatic ARIA-E with a BGTS ≥4 or symptomatic ARIA-E and discontinued for participants with more than 15 ARIA-H or with disseminated leptomeningeal hemosiderosis. In this study, ARIA management rules are based on the Bioclinica 5-point severity score (renamed as Severity Scale of ARIA-E (SSAE) since the writing of the study protocol) and treatment is interrupted for asymptomatic ARIA-E with a Bioclinica score ≥4 or symptomatic ARIA-E of any severity with CNS symptoms attributable to ARIA-E in the judgement of the investigator and discontinued for ARIA-H with disseminated leptomeningeal hemosiderosis. Disseminated leptomeningeal hemosiderosis is defined as more than three focal leptomeningeal hemosiderosis cumulatively.

### 2. STATISTICAL HYPOTHESES

All analyses provided in this document are descriptive, thus no statistical hypothesis will be tested in these analyses.

### 3. SAMPLE SIZE DETERMINATION

The sample size will be determined by the number of participants who complete the parent studies (GRADUATE I and GRADUATE II) and enroll in this study. The sample size is expected to be no more than approximately 2032 participants.

### 4. ANALYSIS SETS

The following analysis sets are defined:

Analysis Set	Definition
All enrolled participants	All enrolled participants (i.e.; who signed the informed consent form and are marked as enrolled in IxRS), whether or not the participant received the assigned treatment.
ITT (intent to treat)	All enrolled participants, who received at least one dose of study drug. Participants will be analyzed by the treatment they were randomized to in the parent studies.
Safety-evaluable (SE)	All participants enrolled who received at least one dose of study drug in this study or in the OLE part of the parent studies. Any participant randomized to placebo in the parent studies who received at least one dose (any dose) of active drug during the double-blind treatment in the parent studies will be summarized as having received the active drug in the parent studies.
MRI safety-evaluable (M-SE)	All participants in the safety-evaluable analysis set who had at least one post-baseline safety MRI scan.
Immunogenicity	All enrolled participants with at least one ADA assessment.
MRI modified intent-to- treat (MRI-mITT)	All participants in the ITT analysis set who had at least one valid volumetric MRI quantitative measurement.
CSF modified intent-to- treat (CSF-mITT)	All participants in the ITT analysis set who had at least one valid quantitative cerebrospinal fluid (CSF) measurement.

Amyloid PET modified ITT (aPET-mITT)	All enrolled participants of the ITT analysis set who consented to the Amyloid PET substudy, did not withdraw consent before enrolment in the substudy and had at least one amyloid PET scan with a valid quantitative measurement.
Tau PET modified ITT (tPET-mITT)	All enrolled participants of the ITT analysis set who consented to the Tau PET substudy, did not withdraw consent before enrolment in the substudy and had at least one tau PET scan with a valid quantitative measurement.

ITT = intent to treat; SE = safety-evaluable; M-SE = MRI safety-evaluable.

### STATISTICAL ANALYSES

#### 5.1 GENERAL CONSIDERATION

The purpose of this study is to assess the safety, tolerability, and efficacy of long-term administration of open-label gantenerumab in participants with AD who completed GRADUATE I or GRADUATE II.

The period of the POSTGRADUATE study and the OLE period from the parent studies will henceforth be referred to as the OLE period. Data from the OLE period, i.e., from OLE baseline (see Section 5.1.1 below for definition) to the end of study, will be summarized. Consequently, for participants who completed the OLE part of the parent studies and gave informed consent for the POSTGRADUATE study, the data collected in the OLE period of the parent studies will be included in the CSR of POSTGRADUATE. This will ensure that data from baseline and uptitration are included in the analyses for all participants of POSTGRADUATE. Participants of the OLE period of the parent studies without informed consent to POSTGRADUATE cannot be included in the analyses for the CSR of POSTGRADUATE and will instead be included in the analyses within the parent studies' CSRs.

All analyses will be purely descriptive and no imputation of missing data will be performed. For continuous data, descriptive statistics of mean, standard deviation, median, 1st and 3rd quartile as well as minimum and maximum and number of available data will be provided. For categorical data, number and frequency will be provided for each category as well as the number of available data.

All analyses of safety endpoints will be based on the SE analysis set unless mentioned otherwise while all analyses of efficacy endpoints will be performed for the ITT analysis set. The immunogenicity analysis set will be used for immunogenicity analyses.

Results will be shown separately based on previous treatment in the GRADUATE parent studies GRADUATE I and GRADUATE II, and by participation / non-participation in the OLE part of the parent studies and overall. For analyses using the ITT analysis set, this will be the treatment as randomized in the parent studies; for analyses using the SE analysis set, this will be the treatment actually received in the parent studies.

The results are shown separately by participation / non-participation in the OLE part of the parent studies to mitigate the introduction of bias into the overall results. The non-inclusion of participants who discontinued during the OLE part of the parent studies and do not have an informed consent to POSTGRADUATE introduces an immortal time bias in certain analyses for this group of participants for the OLE part of the parent studies. The separation is further required due to different ARIA management rules in the parent studies and this study.

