#### 5.2 PARTICIPANT DISPOSITION

The analysis of participant disposition will be based on all enrolled participants (see analysis sets in Section 4). The number of participants enrolled will be tabulated by country and site. Participant disposition (the number of participants enrolled, treated, and completing the study) will be tabulated. Premature study drug discontinuation and study discontinuation, as well as reasons for discontinuations, will be summarized.

Major protocol deviations, including major deviations with regard to the inclusion and exclusion criteria, will be summarized. Separate tables will be provided for COVID-19-related major protocol deviations and reasons for COVID-19-related major protocol deviations.

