#### 5.3 PRIMARY ENDPOINTS ANALYSIS

### 5.3.1 Definition of Primary Endpoints

The primary objective for this study is to evaluate the safety and tolerability of long-term gantenerumab administered by SC injection on the basis of adverse events (AEs), physical examinations, vital signs, ECGs, laboratory tests, C-SSRS, ARIA-E and ARIA-H, ISRs, treatment discontinuations for AEs, and incidence of AEs of special interest.

The corresponding primary endpoints are:

- Nature, frequency, severity, timing, and outcomes of adverse events and serious adverse events
- Physical examinations (including neurologic systems), vital signs, ECG, laboratory tests, and Columbia-Suicide Severity Rating Scale (C-SSRS)
- Nature, frequency, severity, and timing of ARIA-E and ARIA-H

- Nature, frequency, severity, timing, and outcomes of ISRs
- Incidence of treatment discontinuations for adverse events
- Incidence of adverse events of special interest

The analytical approaches are described in pertinent subsection for each endpoint below.

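### For deaths and discontinuations, rollovers from the parent OLE are counted from OLE Day 1 but cannot have the event before about Week 34–36; separate columns leave the parent-OLE and overall figures uncorrected

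*SAP*

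**What the plan says.** SAP 5.1 treats the parent-study OLE and WN42171 as one OLE period running from OLE baseline to end of study. Parent-OLE data are brought in "for participants who completed the OLE part of the parent studies and gave informed consent for the POSTGRADUATE study". For these rollovers the baseline visit is OLE Day 1 of the parent study (Protocol 4.5.2). SAP 5.3.3 counts treatment-emergent AEs from the first OLE dose and takes percentages over the safety-evaluable set. SAP section 4 defines that set as enrolled participants who "received at least one dose of study drug in this study or in the OLE part of the parent studies".

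Entry is restricted. Protocol 4.1.1 and 4.1.2 require completion of the parent part without early discontinuation of study or drug, for any reason. Rollovers have their first dose here about two weeks after OLE Week 34 (Protocol 3.1.1), or later if parent uptitration ran long (notes to Protocol Appendix 1, Table 3).

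SAP 5.1 concedes that leaving out parent-OLE discontinuers "introduces an immortal time bias in certain analyses for this group of participants". Its answer is separate display, "to mitigate the introduction of bias into the overall results", which it also justifies by the "different ARIA management rules in the parent studies and this study". Results nevertheless appear by "participation / non-participation in the OLE part of the parent studies and overall". On disposition, SAP 5.2 states: "Premature study drug discontinuation and study discontinuation, as well as reasons for discontinuations, will be summarized". Sections 5.7.1, 5.7.6.3 and 5.7.7.3 add the distribution of discontinuations by visit window; the last two, for the PET substudies, mention only previous treatment arm as a grouping. Among the primary endpoints in SAP 5.3.1 is: "Incidence of treatment discontinuations for adverse events".

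**The concern.** For most AEs, a rollover can have the event during the parent OLE and it will be counted. Death and permanent withdrawal are different. A participant who died or withdrew in the parent OLE never reaches WN42171 and is missing from the table. Everyone who does reach it brings about 34–36 weeks in which the event was impossible by selection, although the reported period starts at OLE Day 1.

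Showing the two groups side by side does not change a pooled percentage, and it does nothing for the parent-OLE column. Only the non-participation column is free of this bias. In the visit-window tables the early windows will show zeros for rollovers that reflect selection, not safety.

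These are primary safety outputs. Anyone who reads the overall or parent-OLE column as long-term incidence from the start of open-label treatment will understate deaths and AE discontinuations. The first interim analysis, meant to support a potential filing, includes disposition and AEs (SAP 5.8.1), and shorter follow-up makes the event-free share larger.

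**Working it through.** **Entry time, checked against the plan's dose counts.** Protocol 3.2 gives up to 86 doses after uptitration. Dosing every two weeks from Week 36 to Week 206 gives (206 − 36)/2 + 1 = 86. From OLE Day 1 it gives 206/2 + 1 = 104. Both match the dose numbers at Week 206 in Protocol Appendix 1 (Table 5 for rollovers, Table 4 for the others). So 104 − 86 = 18 dosing visits, Weeks 0 to 34, precede a rollover's first dose here: 18/104 = 17.3%.

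**Event-free share of counted time.** Share = E/T, with entry week E and follow-up week T, both from OLE Day 1.

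| | E = 34 | E = 36 |
|---|---|---|
| T = 208 (planned final visit) | 34/208 = 16.3% | 36/208 = 17.3% |
| T = 104 (assumed cut-off) | 34/104 = 32.7% | 36/104 = 34.6% |

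**Illustration of the effect on percentages.** The documents give no rollover share, event rate or interim follow-up length, so these are assumptions: constant hazard h, equal in both groups; rollover share f; everyone followed to T.

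- Risk from OLE Day 1 = 1 − exp(−h·T/52); the non-participation column estimates this.
- Parent-OLE column = 1 − exp(−h·(T − E)/52).
- Overall column = (1 − f) × first + f × second.

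With E = 36 and f = 0.5:

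| h per 100 person-years | T | From Day 1 | Overall | Parent-OLE |
|---|---|---|---|---|
| 2 | 208 | 7.7% | 7.0% | 6.4% |
| 5 | 208 | 18.1% | 16.7% | 15.2% |
| 10 | 208 | 33.0% | 30.6% | 28.2% |
| 2 | 104 | 3.9% | 3.3% | 2.6% |
| 5 | 104 | 9.5% | 7.9% | 6.3% |
| 10 | 104 | 18.1% | 15.2% | 12.3% |

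Letting f run from 0.25 to 0.75, h from 2 to 10 and E from 34 to 36, the overall column shows 87–97% of the risk from Day 1 at Week 208 and 74–92% at Week 104. The parent-OLE column shows 83–86% and 66–69%.

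**Does counting from enrolment repair the rate?** A simulation used 2032 participants, half of them rollovers, entry at Week 34–36 with 20% of rollovers 2–16 weeks later, and 1500 runs. Rates are per 100 person-years in rollovers.

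| True hazard | Counted from Day 1 (Week 104 / 208) | Counted from enrolment (Week 104 / 208) |
|---|---|---|
| 5 in both groups | 3.21 / 4.05 | 5.03 / 5.00 |
| Rollovers 3, others 5 | 1.93 / 2.45 | 3.01 / 3.00 |
| 10 before Week 36, 5 after | – | 5.07 / 5.02 |

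The second row shows that a group-specific rate does not need the two groups to have similar hazards. The third shows its limit: it describes time after enrolment only and says nothing about uptitration.

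**The case against.** The strongest reply is that the SAP already discloses the bias, names the group and the period, and shows the strata. It plans only headcount percentages: no time-to-event curve, no person-time rate and no hypothesis test. The proportion of enrollees who later died or withdrew is a correct number. Parent-OLE participants without consent to this study are assigned to the parent CSRs, and analyses across the double-blind period, the parent OLE and this study are described in a separate document (SAP section 1), so a fuller estimate may exist elsewhere. Most of this stands. It makes the point an incomplete remedy, not a hidden error. It does not tell a reader which tables to distrust, and it does not justify keeping a pooled column in them.

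Three narrower objections also stand.

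- A reader might infer that rollovers can have no counted AE of these kinds with onset before enrolment. That is too strong. An AE that began in the parent OLE and turned fatal, or led to withdrawal, after enrolment is counted. Only the death or the withdrawal itself cannot come earlier.
- Counting from OLE Day 1 is explicit for AEs (SAP 5.3.3). For disposition it follows from the general rule in SAP 5.1; sections 5.2 and 5.7.1 state no time origin.
- Every percentage in the illustration rests on assumed hazards and rollover shares, and Week 104 is not a stated cut-off.

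**Conclusion.** The point holds. For deaths, AEs leading to drug discontinuation, and premature study or drug discontinuation, separate display leaves the parent-OLE and overall columns too low when read as incidence since OLE Day 1. What the documents fix is the event-free share: 16–17% of a rollover's counted time at Week 208. The 33–35% figure applies only if a cut-off falls at Week 104. The effect on the published percentages cannot be computed from the documents.

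A reader might go further and conclude that the safety percentages are wrong, or that primary safety is understated by a third. Neither is supported. The percentages are correct for those enrolled, the pooled effect depends on an unknown rollover share, and no test or stopping decision rests on it. Nor does this mechanism reach other AE tables or ARIA, whose events can occur and be counted before enrolment; they are subject only to ordinary survivor selection. This is a cheap improvement to descriptive primary safety tables whose bias is disclosed but not corrected.

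**What to change.** In SAP 5.1:

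- Name the affected analyses: deaths, AEs leading to study drug discontinuation, and premature study or drug discontinuation, including the visit-window tables in 5.7.1, 5.7.6.3 and 5.7.7.3.
- For these, omit the overall column, or footnote it with the rollover entry time.
- Add exposure-adjusted rates by participation group and previous treatment, with rollovers contributing person-time from WN42171 enrolment. Enrolment is preferable to first dose here, because the safety-evaluable set can include enrollees dosed only in the parent OLE.
- Date events by death or by study or drug withdrawal, not by AE onset. Onset dating would discard AEs that began earlier and ended in death or withdrawal after enrolment.
- In the visit-window tables, mark windows before enrolment as not at risk for rollovers instead of showing zero.
- Give uptitration-period incidence of these outcomes from non-participants only. State that participation was not randomised and that ARIA rules differed, and refer to the parent CSRs for those who stopped during the parent OLE.
- Apply the same rules at the interim analyses.

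The cost is SAP wording and some programming on data already held. The downside is precision, because early incidence rests on non-participants alone. To show the scale with a Week 208 percentage, take 2032 participants, half rollovers, at 5 per 100 person-years. The standard error is √(0.181 × 0.819/1016) = 1.21 points for non-participants and √(0.152 × 0.848/1016) = 1.13 for rollovers. The pooled figure is ½√(1.21² + 1.13²) = 0.83 points.

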1.3.2.1 Amyloid-Related Imaging Abnormalities

ARIAs are one of the most significant adverse events reported in therapies against aggregated forms of A β . These findings appear to be dependent on dose-, time-, and apolipoprotein E gene allele ϵ 4- (APOE ϵ 4-) (Piazza and Winblad 2016).

The mechanism underlying the development of amyloid-related imaging abnormality–edema/effusion (ARIA-E) and amyloid-related imaging abnormality–microhemorrhage/hemosiderin deposition (ARIA-H) during anti-amyloid treatment is not yet fully understood. Because antibodies remove A β from both the parenchyma and cerebral vasculature, vessels with preexisting amyloid vascular pathology might become transiently more susceptible to leakage of vascular contents. This pathology results in ARIA-E if the leakage consists of proteinaceous fluid and in ARIA-H if the leakage consists of blood products (Sperling et al. 2012). An anti-A β therapy that effectively maintains vascular A β clearance would allow vascular remodeling and might, over time, decrease the risk of such extravasation events (Sperling et al. 2012). This is consistent with experiences in previous and ongoing studies and with reported data from the long-term extension study of aducanumab treatment (Viglietta et al. 2016).

Understanding of the clinical significance of ARIA by study sponsors, investigators, and regulators has substantially evolved since ARIA events were first seen on MRI scans in

Gantenerumab—F. Hoffmann-La Roche Ltd 29/Protocol WN42171, Version 4

a Phase I clinical trial with bapineuzumab (Black et al. 2010). The accrued clinical evidence with gantenerumab and other N-terminus anti-amyloid antibodies has shown that ARIA events tend to occur early in treatment, are dose- and APOE ε 4-dependent, and can be monitored by MRI and managed with dose intervention algorithms.

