4.1.2 Exclusion Criteria

Participants who meet any of the following criteria will be excluded from study entry:

• Pregnant or breastfeeding, or intending to become pregnant during the study or within at least 16 weeks after the final dose of study drug

Women of childbearing potential must have a negative urine pregnancy test at the final visit of the parent study.

- Prematurely discontinued from Study WN29922 or WN39658, either its double-blind or OLE part, as applicable, or from study drug, for any reason
- Any medical condition that the investigator or Sponsor determines may jeopardize the participant's safety if he or she continues to receive study treatment
- Received any investigational treatment other than gantenerumab during or since completion of Study WN29922 or WN39658, either its double-blind or OLE part, as applicable
- Evidence of disseminated leptomeningeal hemosiderosis (i.e., more than three focal leptomeningeal hemosiderosis)
- Evidence of intracerebral macrohemorrhage
- Use of prohibited medication (see Section 4.4.2)
- Evidence of ARIA-E on the last MRI scan report in Study WN29922 or WN39658, either its double-blind or OLE part, as applicable

Participants should remain in the parent study, as governed by that protocol, and may enroll in this study once the ARIA-E is resolved.

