### 5.3.4 Magnetic Resonance Imaging Safety Findings

ARIA-E and ARIA-H are identified risks associated with gantenerumab. Sites were asked to capture ARIA findings as AEs in the POSTGRADUATE eCRF if they met any of the following criteria:

- Symptomatic ARIA-E (onset or worsening of CNS symptom[s] attributable to ARIA-E MRI findings in the judgement of the investigator), and/or
- ARIA findings that result in a change in study treatment (e.g., dosage modification, treatment interruption, or treatment discontinuation), and/or
- · Findings that are otherwise clinically significant in the investigator's judgment

Not all ARIA MRI findings qualify as AE. ARIA analyses will be mainly based on ARIA MRI findings. ARIA AEs will also be reported. ARIA analyses will be restricted to ARIAs documented during this study or the OLE part of the parent studies.

Based on MRI data, the incidence, severity (based on the Bioclinica severity scale (see Appendix 2) and the Barkhof Grand Total Score [BGTS]) and timing of ARIA-E and the incidence and timing of ARIA-H will be summarized overall and also by APOE  $\epsilon$ 4 genotype (by number of alleles) and by dose level. For participants from the OLE part of the parent studies, only ARIA-E severity measured by the BGTS is available for events that occurred during the OLE part of the parent studies. The timing of ARIA-E and ARIA-H may be summarized by descriptive statistics. Recurrence of ARIA-E within this study or the OLE part of the parent studies will be summarized. ARIA-E with associated and attributable CNS symptoms (see Section 5.3.4.1) and serious associated and attributable CNS symptoms will be summarized overall and also by APOE  $\epsilon$ 4 genotype (by number of alleles). Temporal co-occurrence of ARIA-E and ARIA-H will be summarized overall and also by APOE  $\epsilon$ 4 genotype. Temporal co-occurrence is defined as an MRI scan showing new ARIA-H that occurs between ARIA-E onset and resolution (inclusive), irrespective of the brain region.

MRI findings other than ARIA will also be summarized.

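### SAP 5.1's split by parent-OLE participation leaves two ARIA rule sets mixed in the rollover and overall columns, and SAP 5.3.4 specifies no analysis by dosing action or on-study ARIA-H count

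*SAP*

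**What the plan says.** SAP 1.2.4 (and, in near-identical terms, Protocol 1.3.2.1) says that "the Sponsor intends to examine the safety of continuing gantenerumab treatment through mild to moderate asymptomatic ARIA-E findings", and likewise the safety of treatment when the number of microhemorrhages is higher than was previously allowed.

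SAP 1.2.4 sets out both rule sets. The parent-study rule interrupted drug for those "with asymptomatic ARIA-E with a BGTS ≥4 or symptomatic ARIA-E and discontinued for participants with more than 15 ARIA-H". A further ground for stopping permanently there was disseminated leptomeningeal hemosiderosis. For WN42171 the SAP says that "treatment is interrupted for asymptomatic ARIA-E with a Bioclinica score ≥4 or symptomatic ARIA-E of any severity". The ARIA-H count limit is gone, and only disseminated hemosiderosis leads to discontinuation.

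SAP 5.1 combines the parent OLE and WN42171 into one OLE period. It shows results by previous treatment, by participation in the parent OLE, and overall. It gives two reasons for the participation split: an immortal-time bias, and the ARIA rules ("The separation is further required due to different ARIA management rules in the parent studies and this study").

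SAP 5.3.4 defines the period covered: "ARIA analyses will be restricted to ARIAs documented during this study or the OLE part of the parent studies". It plans:

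- incidence, severity (Bioclinica and BGTS) and timing of ARIA-E;
- incidence and timing of ARIA-H;
- breakdowns of these by APOE ε4 genotype and by dose level;
- recurrence of ARIA-E;
- ARIA-E with attributable, and with serious attributable, CNS symptoms;
- ARIA-E/ARIA-H co-occurrence, and ARIA reported as adverse events.

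**The concern.** The management rule belongs to a study period, but the SAP's split belongs to the participant. A participant who completed the parent OLE was managed under the parent rules up to entry and under the new rules afterwards, and both periods fall in the same column. The split therefore cannot do, for that column or the overall column, the job that SAP 5.1 gives it.

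Separately, the newly permitted exposure is never isolated. SAP 5.3.4 does not say what happened after ARIA-E episodes in which dosing went on, nor in participants treated with more than 15 microhemorrhages.

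ARIA is a primary safety endpoint, and Protocol 3.3.4 asserts that the new management strategy is neutral for participant risk. A pooled ARIA table could be cited in support of dosing through when it contains an unstated share of episodes handled under the parent rules.

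**Working it through.** **Step 1. How much rollover time falls under the parent rules.** Inputs: first WN42171 dose about 2 weeks after the OLE Week 34 visit, so about Week 36 (Protocol 3.1.1); last dose at Week 206 and final visit at Week 208 (Protocol 3.1.1); dosing visits every 2 weeks (Protocol 4.3.2).

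- Visits Day 1 to Week 34: 34/2 + 1 = 18.
- Visits Week 36 to Week 206: (206 − 36)/2 + 1 = 86. This reproduces the up-to-86 doses in Protocol 3.2 and dose number 86 at Week 206 in Appendix 1, Table 5.
- Total: 18 + 86 = 104, which matches dose number 104 at Week 206 in Appendix 1, Table 4.
- Share under parent rules: 18/104 = 17.3% of dosing visits; 36/208 = 17.3% of weeks.

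**Step 2. What that share means for events.** It is a share of time, not of ARIA. For former placebo participants those weeks are the whole uptitration, and Protocol 1.3.2.1 says "ARIA events tend to occur early in treatment". The documents give no rates by period. If the ARIA rate before Week 36 is r times the later rate, with full follow-up, the parent-rule share is 36r/(36r + 172), since 208 − 36 = 172. At r = 1 this is 17.3%. It reaches one half at r = 172/36 = 4.8. Any r above 1 puts it above 17%. For former active participants, already treated for about 2 years, the early-treatment argument does not apply.

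**Step 3. What each column contains.**

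| Column | Rules covering its ARIA |
|---|---|
| Not in parent OLE | New rules only, including full uptitration of former placebo participants |
| Parent-OLE rollovers | Parent rules to about Week 36, new rules after |
| Overall | Both |

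**Step 4. What separates the periods indirectly.**

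- SAP 5.3.4 says that only BGTS exists for parent-OLE events. A Bioclinica severity table for rollovers therefore shows WN42171 ARIA-E only. It does not help for ARIA-H, recurrence, symptoms or co-occurrence.
- In former placebo rollovers, events at 120 mg and 255 mg belong to the parent OLE. The SAP does not say whether 510 mg every 4 weeks and every 2 weeks are distinguished. Former active rollovers are not separated by dose at all.
- SAP 5.8.1 drops the dose-level and time-to-onset analyses from the planned interim analyses.

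**Step 5. Whether any specified analysis uses dosing action or ARIA-H count.**

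- SAP 5.3.3 summarizes adverse events leading to interruption, delayed uptitration or discontinuation. These are the episodes in which treatment changed. Under Protocol 5.3.5.2, an asymptomatic finding with no treatment change need not be an adverse event unless the investigator judges it clinically significant.
- The only cumulative ARIA-H count is the baseline characteristic in SAP 5.7.2, taken from the screening and double-blind part of the parent studies. It covers neither the parent OLE nor WN42171.

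The SAP text therefore specifies no analysis of either stated aim.

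**The case against.** Several points on the other side stand.

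- The split does achieve something. Non-participants are a clean new-rule group, and the immortal-time reason is independent of the ARIA rules. A reader might infer that the split is useless for ARIA; that goes too far.
- The rules overlap. Asymptomatic ARIA-E with BGTS below 4, and ARIA-H counts up to 15, did not stop dosing in the parent studies either. A reader might infer that much of the parent-OLE ARIA reflects episodes in which drug was stopped. The documents give no figure for that, and Protocol 1.3.2.3 describes ARIA-E in earlier gantenerumab studies as mostly mild and asymptomatic.
- A reader might infer that nobody enters with more than 15 ARIA-H, because entry is barred to anyone "Prematurely discontinued from Study WN29922 or WN39658, either its double-blind or OLE part, as applicable, or from study drug, for any reason". Protocol 4.1.2 sets no ARIA-H count limit, however. Under Protocol 4.5.2 a reused parent MRI must follow the last parent dose, so a count first passing 15 on that scan left no parent dose to discontinue.
- The aim stands in background and design text, all analyses are descriptive (SAP 2), and the iDMC reviews ARIA unblinded (Protocol 5.1.2.1).
- Output layouts are deferred to Data Analysis Plan Modules 2 and 3 (SAP 1), which are not available here. A reader might infer that no such table exists anywhere; only its absence from the SAP text can be shown.

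None of this repairs the mixed columns. Many relevant outcomes are already planned, but they are not linked to dosing action or ARIA-H count. Layout documents format analyses; the SAP is where these would be specified.

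**Conclusion.** The point holds within those limits. The participation split does not deliver the rule separation that SAP 5.1 claims for it in the rollover and overall columns, where about 17% of a rollover's scheduled OLE time falls under the parent rules. The share of ARIA events under those rules cannot be computed from the documents. It is likely above 17% in former placebo rollovers. No analysis specified in SAP 5.3.4 reports outcomes by dosing action or by on-study cumulative ARIA-H count.

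This rests on three assumptions: the parent rules applied throughout the parent OLE, as SAP 5.1 implies; rollovers enter near Week 36; and follow-up runs to Week 208. Longer uptitration or earlier termination would raise the share. The number of rollovers is not given. The gap concerns what the report can show about the stated aim. It does not put the other safety summaries in doubt or bear on which management rule is appropriate.

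**What to change.** Add the following to SAP 5.3.4, all descriptive:

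1. Within the rollover stratum and the overall column, show ARIA by onset before versus on or after the first WN42171 dose. This also confines the parent-OLE time affected by immortal-time bias to its own part of the table. Keep the split in the interim outputs.
2. Add an episode-level table of asymptomatic ARIA-E with onset in WN42171 and Bioclinica 1-3, by phase (uptitration or target dose) and actual dosing action. The phase is needed because Protocol Appendix 2 has scores 2-3 continue without uptitration in one phase and on schedule in the other. Flag BGTS of 4 or more where that score is available, since that is the newly permitted exposure. Report later peak severity, conversion to symptomatic, serious adverse events, new ARIA-H or leptomeningeal hemosiderosis, and time to resolution.
3. Show the same safety outcomes for participants dosed in WN42171 with cumulative ARIA-H above 15, whether that count was passed before entry or on study.

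The inputs are already collected: 4-weekly MRI after ARIA-E, dosing records, the CNS symptom form and the adverse event page. The cost is SAP wording and about three tables. Some cells will be small, and at target dose the interrupted row will mostly hold departures from the rule, so the table describes the course of episodes and is not a comparison of strategies.
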